2.10.1.2 Subject ADA status

Any IG sample collected after 150 days of the last dose of PDR001, LAG525, or Canakinumab will not be used for summaries or derivations and will only be included in the listing.

Subject ADA status is defined as follows:

- *Treatment-induced ADA-positive subject*: subject with ADA-negative sample at baseline and at least one treatment-induced ADA-positive sample.
- *Treatment-boosted ADA-positive subject*: subject with ADA-positive sample at baseline and at least one treatment-boosted ADA-positive sample.
- *Treatment-unaffected ADA-positive subject*: subject with ADA-positive sample at baseline, no treatment-boosted ADA-positive samples, and at least one treatment-unaffected ADA-positive sample.
- *Treatment-reduced ADA-positive subject*: subject with ADA-positive sample at baseline and at least one post baseline determinant sample, all of which are ADA-negative samples.
- *ADA-negative subject*: subject with ADA-negative sample at baseline and at least one post baseline determinant sample, all of which are ADA-negative samples.
- *Inconclusive subject*: subject who does not qualify as treatment-induced ADA-positive, treatment-boosted ADA-positive, treatment-unaffected ADA-positive, treatment-reduced ADA-positive, or ADA-negative.

The following summaries of ADA subject status (n and %) will be provided using *Immunogenicity incidence set*:

- Treatment-boosted ADA-positive subjects; denominator is the number of subjects with ADA-positive sample at baseline.

- Treatment-induced ADA-positive subjects; denominator is the number of subjects with ADA-negative sample at baseline.
- ADA-negative subjects: denominator is the number of subjects in *Immunogenicity incidence set*.
- ADA-positive subjects (i.e. ADA incidence): calculated as the number of treatment-boosted ADA-positive and treatment-induced ADA-positive subjects; denominator is the number of subjects in *Immunogenicity incidence set*.

Listings will be provided of subject ADA status.

[REDACTED]

2.11 Patient-reported outcomes

Not applicable.

2.12 Biomarkers

2.12.1 Introduction

As a project standard, Novartis Oncology Biostatistics will analyze only biomarkers collected in the clinical database. The biomarker analysis covered within the SAP pertains mainly to the secondary objective endpoint of determining the proportion of subjects with a favorable biomarker profile (pFBP, [Table 1-1](#) and [Table 2-18](#)).

[REDACTED]

[REDACTED]

[REDACTED] For example, there may be inadequate sample number, issues related to the quality of the sample or issues related to the assay that preclude analysis. Alternatively, there may be insufficient efficacy to allow for correlative analyses. Therefore, depending on the results obtained during the study, collection/analysis of some samples may be omitted.

[REDACTED]

2.12.2 Secondary biomarker objectives

Changes in phenotype and/or activation of T cell populations in the tumor and tumor microenvironment will be analyzed on an on-going basis as part of the secondary objectives (Table 1-1 and Table 2-18). Every effort will be made to make this data available for internal decision making purposes. Such analyses may include, but are not limited to number of CD8⁺ T cell infiltration, T cell activation level by IHC, gene expression analysis, and T cell repertoire/clonality by TCR-sequencing (Table 2-18).

Table 2-18 Parameter definitions for categorization of biomarker outcome at subject level

Biomarker parameter	Analysis	Criteria for favorable biomarker result
Number of tumor infiltrating T cells (TILs)	Changes of CD8 ⁺ T cell numbers as assessed by IHC in tumor/ tumor microenvironment with treatment	Increase
Activation level of TILs	Change of T cell activation marker level(s) as assessed by IHC in tumor/tumor microenvironment with treatment	Increase
TIL repertoire/specificity of T cell response to tumor	TCR clonality changes as assessed by TCR-sequencing in tumor/tumor microenvironment with treatment	Increase
Changes in immune response gene expression signatures	Changes in expression of genes and/or gene signatures as assessed by mRNA analysis in tumor/tumor microenvironment with treatment	Defined per gene/gene signature

2.12.3 Biomarker data

As a project standard, Novartis Oncology Biostatistics will analyze only biomarkers collected in the clinical database. The biomarker analysis covered within the SAP pertains mainly to the secondary objective endpoint of determining the proportion of subjects with a favorable biomarker profile (pFBP, Table 1-1 and Table 2-18).

The biomarker analysis set, as it pertains to the secondary objectives (Table 1-1) as well as the analysis of the change in LAG-3 expression levels, consists of all subjects in the safety set with an evaluable baseline tumor biopsy sample and at least one evaluable post-baseline tumor biopsy sample.

Table 2-19 summarizes the biomarker collection schedules and sample types which are in scope with this SAP.

Table 2-19 Sample biomarker summary table

Biomarker parameter	Biomarker analysis measurement	Time point	Sample	Method	Dataset
Number of TILs	Percent of tumoral CD8 ⁺ cells	Screening Btw, C1D1 and C2D1*	Newly obtained tumor biopsy	IHC	B1

Biomarker parameter	Biomarker analysis measurement	Time point	Sample	Method	Dataset
Activation level of TILs	Percent of tumoral GzmB+ within CD8+cells	Screening Btw, C1D1 and C2D1*	Newly obtained tumor biopsy	FIHC/AQUA	B1
Activation level of TILs	Percent of tumoral CD8+ within Ki67+ cells	Screening Btw, C1D1 and C2D1*	Newly obtained tumor biopsy	FIHC/AQUA	B1
TIL repertoire/ specificity of T cell response to tumor	TCR clonality	Screening Btw, C1D1 and C2D1*	Newly obtained tumor biopsy	TCR sequencing	B1
Changes in immune response gene expression signatures	Gene signature expression levels	Screening Btw, C1D1 and C2D1*	Newly obtained tumor biopsy	Nanostring	B1

2.12.4 General data handling and preprocessing

The mean of all pre dose assessments (i.e. screening and Cycle 1 Day 1 assessments) will be used as the baseline value. The on-treatment assessment will be the result from the tumor biopsy taken between C1D21 and C2D1.

When more than one biomarker data value are available for a subject at any time point, the mean of the replicate values will be used for all statistical analyses.

2.12.5 Secondary biomarker objectives

The secondary objective biomarker data will be listed for each subject for all time points (baseline and on treatment) and ordered by the treatment arm. Absolute and relative change (percent change) from baseline of each biomarker parameter will be calculated for each patient and summarized for each treatment arm. Graphical presentations of the change and percentage change from baseline will be produced via spaghetti plots and boxplots and ordered by the treatment arm.

2.12.5.1 IHC for quantifying tumor infiltrating T cells (TILs)

The number of TILs at each timepoint will be assessed by measuring % CD8+ cells within the invasive margin, tumor and stroma area (as defined by Melamask staining), using the following variables provided in the raw data:

- Intraepithelial tumor (IE) CD8+ density (% of cells containing CD8)
- Intrastroma (IST) CD8+ density
- IST CD8+ density 0 to 10 μm (% of CD8+ IST cells within the 0 to 10 μm region of the IE-IST border)
- IST CD8+ density >10 to 20 μm
- IST CD8+ density >20 to 30 μm
- IST CD8+ density >30 to 40 μm
- IST CD8+ density >40 to 50 μm

For all CD8 parameters above, the baseline value, on-treatment (C1D21-C2D1) value, and the difference from baseline to on-treatment will be listed for each individual patient by treatment arm. The mean, standard deviation, %CV, median, minimum, maximum, inter-quartile range and number for all patients (regardless of treatment arms) will be reported for baseline and change from baseline to on-treatment by combination arm. Inter-quartile range is the number of data points between the 25th and 75th percentile.

The proportion of GzmB+ T cells and Ki67+ T cells will be assessed using FIHC and AQUA at each timepoint. The % of GzmB+CD8+ and Ki67+CD8+ cells within the invasive margin, tumor and stroma area (as defined by Melamask staining) will be calculated using the following variables provided in the raw data:

- IE CD8+Ki67+ density (% of CD8+cells containing Ki67)
- IST CD8+Ki67+ density
- IE CD8+GzmB+ density (% of CD8+cells containing GzmB)
- IST CD8+GzmB+ density

The GzmB+ density is expected to be low but unique to T cells. In instances where the density is <10%, the following raw data variables may be employed in lieu of the one above for all samples within a particular analysis:

- IE GzmB+ density (% of cells containing GzmB)
- IST GzmB+ density (% of cells containing GzmB)

For all parameters above, the baseline value, on-treatment value, and the difference from baseline to 3-4 weeks will be listed for each individual patient by treatment arm. The mean, standard deviation, %CV, median, minimum, maximum, inter-quartile range and number for all patients (regardless of treatment arms) will be reported for baseline and change from baseline to on-treatment (C1D21-C2D1) by combination arm. Inter-quartile range is the number of data points between the 25th and 75th percentile.

2.12.5.2 TCR sequencing for quantifying T cell clonality

T cell clonality is calculated as follows:

1 – (normalized Shannon entropy)

Using the following variable provided in the raw data:

- Normalized Shannon entropy.

2.12.5.3 Nanostring for quantifying gene expression signatures

Gene expression data will be calculated using the following variables provided in the raw data:

- raw gene expression
- housekeeper-gene normalized gene expression

The gene signatures that will be scored for expression are defined in [Table 2-20](#). The score of each gene signature will be calculated using the simple average of log expression values for all genes. The aggregate score for the three gene signatures, calculated as average of the score of each gene signature will be used as one of the criteria for favorable biomarker result. Additional genes may be considered for gene expression analyses pertaining to biomarker outcomes.

Table 2-20 Immune response gene expression signatures

Signature	Gene names									
T-cell inflamed [Ayers, 2017]	CD3D	IDO1	CIITA	CD3E	CCL5	GZMK	CD2	HLA-DRA	CXCL13	IL2RG
	NKG7	HLA-E	CXCR6	LAG3	TAGAP	CXCL10	STAT1	GZMB		
CD8 T-cell	CCL5	CTSW	FASLG	CD8B	ZNF683	GZMA	XCL2	CD7	KLRC1	CD8A
	XCL1	TRDC	NKG7	KLRK1	GNLY	PRF1	GZMB	GZMH	LAG3	KLRD1
IFN-gamma	IFNG	CXCL9	CXCL10	CXCL11	GBP1					

For all parameters above, the baseline value, on-treatment (C1D21-C2D1) value, and the difference from baseline to 3-4 weeks will be listed for each individual patient by treatment arm. The mean, standard deviation, %CV, median, minimum, maximum, inter-quartile range and number for all patients (regardless of treatment arms) will be reported for baseline and change from baseline to on-treatment by combination arm. Inter-quartile range is the number of data points between the 25th and 75th percentile. Calculation of proportion of patients with favorable biomarker profile

The biomarkers listed in [Table 2-20](#) will be used to calculate the proportion of subjects with a favorable biomarker profile (pFBP).

- As for the parameter of number of tumor infiltrating T cells (TIL), an increase from baseline to on-treatment (C1D21-C2D1) in the IE CD8+ density is considered a favorable change. Whether such increases are accompanied by a decrease in IST CD8+ density may be taken into consideration as a signal for CD8+ T cell migration into the tumor. Furthermore increases in CD8+ density in IST areas closer to the IE-IST border (e.g. an increase in 0-10 μm and >10-20 μm regions compared to more distal regions, >30 μm) may be taken into consideration as another signal for CD8+ T cell migration into the tumor
- As for the activation level of TIL, an increase from baseline to on-treatment in percentage of GzmB+ T cells is considered favorable. In the presence or absence of an increase in GzmB+ T cells, an increase in percentage of Ki67+ T cells is also considered favorable. If decreases in both GzmB + T cells and Ki67+ T cell are observed, this parameter would not be considered favorable.

- As for the TIL repertoire/specificity of T cell response to tumor, an increase from baseline to on-treatment in TCR clonality is considered favorable.
- An increase from baseline to on-treatment in the aggregate gene signature score would be considered favorable.

For each biomarker involved in the evaluation of pFBP as stated above, the baseline, 3-4 weeks biomarker values, and the difference from baseline to 3-4 weeks will be listed for each individual patient by combination arm. The mean, standard deviation, %CV, median, minimum, maximum, inter-quartile range and number for all patients (regardless of treatment arms) will be reported for baseline and change from baseline to 3-4 weeks by combination arm. Inter-quartile range is the number of data points between the 25th and 75th percentile.

If an individual subject has two or more favorable biomarker parameters from [Table 2-16](#) then that subject will be considered to have a favorable biomarker profile.

For each combination arm, the proportion of subjects with a favorable biomarker profile (pFBP) are then defined as the number of subjects with favorable biomarker profiles divided by the number of subjects enrolled into the arm which are included in the biomarker analysis set for that particular interim analysis and will be summarized.

[REDACTED]

[REDACTED]

[REDACTED]

[REDACTED]

[REDACTED]

[REDACTED]

[REDACTED]

[REDACTED]

[REDACTED]

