1.1.1 Study design: Part 1: Selection phase

The primary objective of part 1 is to evaluate the preliminary ORR of spartalizumab in combination with novel agents in patients with previously treated unresectable or metastatic melanoma.

As dose regimens for additional new combinations with spartalizumab become established, new combination arms will be added under the same master protocol through protocol amendments. A maximum of 10 arms may be active (open to enrolment) at any given time under this master protocol, and any arms active in part 1 will continue to be randomized with equal probability.

At each interim analysis, it will be determined which arm(s) (1) is declared efficacious and will be expanded to part 2, (2) will continue enrolment in part 1 (up to a maximum of 45 subjects enrolled in a given arm) or (3) will be dropped for futility, taking into account all available efficacy, safety and biomarker data. If a combination arm can be expanded to part 2, the exact sample size for part 2 will be determined at that time when the decision to expand this arm is taken (refer to Section 10.8 of the protocol for further details on sample size considerations). The timing of interim analyses and the criteria used for decision-making at each interim analysis are detailed in [Section 1.1.3](#) and Section 10 of the protocol.

Further discussion on the study design for part 1 can be found in Section 4.1 of the protocol.

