2.12.5.3 Calculation of pFBP

The biomarkers listed in [Table 2-3](#) will be used to calculate the proportion of subjects with a favorable biomarker profile (pFBP).

For each biomarker involved in the evaluation of pFBP as stated above, the baseline, 3-4 weeks biomarker values, and the absolute difference from baseline to 3-4 weeks will be listed for each individual subject by combination arm. The mean, standard deviation, %CV, median, minimum, maximum, inter-quartile range and number for all subjects (regardless of treatment arms) will be reported for baseline and change from baseline to 3-4 weeks by combination arm. Inter-quartile range is the number of data points between the 25th and 75th percentile.

If an individual subject has two favorable biomarker parameters from Table 2-3 then that subject will be considered to have a favorable biomarker profile. A favorable biomarker will be defined as follows:

Number of tumor infiltrating T cells (TIL) as measured by CD8 IHC:

- An increase from baseline to on-treatment (C1D21-C2D1) in the IE CD8+ density is considered a favorable change as follows:
 - IE CD8 increase which is $\geq 1\%$ in magnitude (i.e. [on-treatment C1D21-C2D1 %IE value] – [baseline IE value] = $\geq 1\%$)

And

- Percent fold change in IE is $\geq 30\%$ (i.e. ([on-treatment C1D21-C2D1 %IE value] – [baseline IE value])/[baseline IE value] = $\geq 30\%$)

Changes in immune response gene expression signature as measured by Nanostring:

- For baseline to on-treatment changes in the TIS score, the following would be considered favorable:
 - ≥ 1.5 fold change (i.e. on-treatment aggregate gene signature score)/[baseline aggregate gene signature score]

For each combination arm, the proportion of subjects with a favorable biomarker profile (pFBP) are then defined as the number of subjects with favorable biomarker profiles divided by the number of subjects enrolled into the arm which are included in the paired biomarker analysis set for that particular interim analysis and will be summarized.

[REDACTED]

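### In the main SAP any rise is favorable and two of four parameters suffice, so with no treatment effect 50–78% of fully assayed patients would have a favorable biomarker profile

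*SAP*

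**What the plan says.** The rule stands at the end of section 2.12.5.3 of the main SAP (the SAP for the randomized section):

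- **CD8.** An increase "in the IE CD8+ density is considered a favorable change".
- **Activation, first route.** "an increase from baseline to on-treatment in percentage of GzmB+ T cells is considered favorable".
- **Activation, second route.** Whether or not GzmB rises, "an increase in percentage of Ki67+ T cells is also considered favorable". The parameter is ruled out only in one case: "If decreases in both GzmB + T cells and Ki67+ T cell are observed, this parameter would not be considered favorable".
- **TCR clonality.** "an increase from baseline to on-treatment in TCR clonality is considered favorable".
- **Gene expression.** Any increase in the aggregate score of three signatures is favorable.
- **Profile.** "If an individual subject has two or more favorable biomarker parameters from" the table, the patient has a favorable profile. The sentence points to Table 2-16 and the opening of the pFBP text to Table 2-20, but the four parameters are listed in Table 2-18.

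No minimum change and no reference value for pFBP appears in the visible text. pFBP is a secondary endpoint (Table 1-1). Its denominator is tied to the biomarker analysis set at each interim analysis. Section 1.1.1 says that arms are expanded, continued or dropped "taking into account all available efficacy, safety and biomarker data".

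The Arm 1A SAP, in its own 2.12.5.3, opens its criteria with "A favorable biomarker will be defined as follows". It then requires an intraepithelial CD8 rise of at least 1% in magnitude and at least 30% relative, and a T-cell inflamed signature change of at least 1.5-fold. Its 2.12.3 requires evaluable results for two or more parameters.

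**The concern.** Repeat biopsies and assays vary even when nothing has changed biologically. With a threshold of zero, a marker that carries only noise rises about as often as it falls. The rule then makes chance success easier in two ways: activation has two routes, and only two of four parameters are needed. A majority of patients can therefore qualify with no drug effect, and the SAP gives the reader no background rate to set against the result.

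The numbers at the interims are small. The first one takes about 10 subjects per arm (1.1.3). If all 10 had paired, fully assayed biopsies and the chance rate were 65%, an arm without effect would show six or more favorable patients about 75% of the time.

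**Working it through.** The SAP states no expected or null value for pFBP, so there is no figure of its own to reproduce.

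**Inputs.** From the main SAP, 2.12.5.3: four parameters; favorable means any rise; activation is met by GzmB or Ki67; two or more are needed. Assumptions, not in the documents: no treatment effect, a chance of 0.5 that each marker rises, few ties, all four parameters evaluable. Correlation between markers is varied because the SAP gives none.

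**1. Independent changes.**

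- Activation: 1 − 0.5 × 0.5 = 0.75. The other three: 0.5 each.
- P(none) = 0.5³ × 0.25 = 0.031.
- P(exactly one) = 3 × 0.5³ × 0.25 + 0.5³ × 0.75 = 0.094 + 0.094 = 0.188.
- P(two or more) = 1 − 0.031 − 0.188 = **78.1%**.
- If activation rested on one marker, the figure would be 11/16 = 68.75%.

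**2. Correlated changes.** Five equicorrelated normal changes, one million simulated patients per value:

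| Correlation | Chance pFBP, either-marker rule |
|---|---|
| 0 | 78.1% |
| 0.3 | 69.5% |
| 0.5 | 65.1% |
| 0.8 | 58.5% |
| 0.9 | 55.8% |
| 1 (limit) | 50% |

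At correlation 0.5 there is an exact check. Given the shared factor, each marker rises with a probability p that is uniform on 0 to 1.

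- P(none) = ∫(1−p)⁵dp = 1/6.
- P(exactly one) = ∫[3p(1−p)⁴ + (1−p)³ − (1−p)⁵]dp = 1/10 + 1/4 − 1/6 = 0.183.
- P(two or more) = 1 − 0.167 − 0.183 = 65.0%.

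**3. Fewer evaluable parameters.**

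- Three, none of them activation: 50%, at any correlation by symmetry.
- Three, including activation: 62.5% if independent, 52.6% at correlation 0.9.
- Two single-marker parameters: 0.25 + arcsin(ρ)/(2π), which is 25% at ρ = 0, 33% at 0.5 and 43% at 0.9.
- Activation plus one other: 0.75 × 0.5 = 37.5% if independent.
- With two parameters, the limit at perfect correlation is 50%.

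**4. Ties.** If ties cut the chance of a rise to 0.40 per marker, activation is 1 − 0.6² = 0.64. Then P(none) = 0.6³ × 0.36 = 0.078, P(exactly one) = 3 × 0.4 × 0.6² × 0.36 + 0.6³ × 0.64 = 0.294, and P(two or more) = 62.9% (independent changes, four evaluable).

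**5. What a minimum change could do.** If four independent parameters each met a stricter criterion by chance with probability 0.20, P(two or more) = 1 − 0.8⁴ − 4 × 0.2 × 0.8³ = 18.1%. At 0.10 it is 5.2%. Both probabilities are illustrative assumptions.

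**The case against.** Five points can be made in the plan's favor.

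**Not every patient will have four results.** Section 2.12.1 expects sample and assay failures. The Arm 1A SAP (2.12.2) drops TCR sequencing for low assay success and may drop activation. GzmB density is expected to be low (main SAP 2.12.5.1), so ties are plausible. This stands. A reader might infer that an inert arm would simply show 56–78%; that holds only with four evaluable parameters and few ties, and even then 56% is not a floor.

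**Some text is blacked out.** There are redactions after the biomarker set definition (2.2) and after the pFBP definition. An evaluability rule may be there. The definition of a favorable change is visible and complete.

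**No decision hangs on pFBP alone.** It has no test or cut-off. Table 2-9 uses ORR only, and 2.5.2 makes ORR the main basis for selection, with biomarkers considered alongside. The size of each change will also be listed and plotted. This stands: a reader might infer that a high pFBP would be taken as proof of activity, but the SAP does not say so.

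**Comparability with Arm 1A.** One might expect the fix to make pFBP comparable between the two SAPs. It would not: Arm 1A has no TCR clonality, may lack activation, uses one signature instead of three, and enrolls LAG-3 positive patients.

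**Thresholds for the other parameters.** One might extend the 30% rule to activation and clonality, or insist on a single activation marker. Neither has support in the documents. Arm 1A sets no threshold for either parameter, and the main SAP accepts either marker explicitly.

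None of this supplies a minimum change or a reference level.

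**Conclusion.** The point holds as a weakness in how a secondary endpoint is defined. Under no effect, with a 50% chance of a rise, few ties and four evaluable parameters, chance alone gives a pFBP of 78% (independent changes), about 65% (correlation 0.5) or 56% (0.9), and never below 50% over non-negative correlations. With three evaluable parameters the range is about 50–63%, with two about 25–50%. The background level thus depends on assay success as well as on correlation, and an observed pFBP cannot be interpreted without it.

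These figures do not describe a false-positive rate for the trial, and they leave the ORR decision rules untouched. What is affected is the information that pFBP can add to the biomarker part of the selection decision. The sponsor's later Arm 1A SAP shows that minimum changes were judged workable for CD8 and gene expression.

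**What to change.** In the main SAP, 2.12.5.3 and Table 2-18:

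1. Apply the Arm 1A minimum for intraepithelial CD8: a rise of at least 1 percentage point and at least 30% relative.
2. Require a gene-score change equivalent to at least 1.5-fold. The main SAP score is an average of log expression with no base given, so state the base and apply the criterion as a difference: log(1.5) is 0.585 in base 2, 0.405 in natural logs and 0.176 in base 10.
3. Pre-specify minimum changes for activation and TCR clonality from assay or replicate variability.
4. Require at least two evaluable parameters for the pFBP denominator, as in Arm 1A, unless blacked-out text already does so.
5. Beside the observed pFBP for each arm, print the chance-level value for the parameters actually evaluable, with its assumptions.
6. Correct the references to Tables 2-16 and 2-20.

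The cost is SAP wording, re-derivation from data already collected, and a lower reported pFBP. If the rule is also fixed in the protocol, section 4 of the main SAP should list the change.
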